## 7.8. Subgroups

While this study is not powered for subgroup analyses, the primary and secondary efficacy endpoints will be analyzed by defined subgroups. Additional subgroups may be added as the data dictate, and subgroup analysis may be performed on other variables. If the total number of subjects in a subgroup is < 10% of the total number of randomized subjects, the analysis for that subgroup may not be performed.

Assessment of safety by subgroups will be performed for OTAEs.

- UPDRS based on baseline score
  - UPDRS  $\leq 10$  and  $>10$
  - UPDRS  $<$  Baseline Overall Median and  $\geq$  Baseline Overall Median (using overall SAFETY Population)
- Cognitive Severity based on baseline MMSE
  - 14-19 and 20-26
- Geographic Region
  - US
  - EU and Canada (English speaking)
  - All other Europe (non-English speaking)
- Age (years)
  - $<$  Median and  $\geq$  Median (using overall SAFETY Population)
  - $<65$  and  $\geq 65$
- Gender
  - Female and Male
- Race
  - White and Non-White. Not that a few patients may be excluded from this analysis as their country privacy laws prohibit collection of race.
- Ethnicity

- Hispanic and Not Hispanic
- Use of Acetylcholinesterase medications
  - Using AChEIs vs Not Using AChEIs
  - Using Donepezil
  - Using Rivastigmine
- Use of Anti-parkinsonian medications (including but not limited to L-dopa, dopamine agonists, and monoamine oxidase inhibitors)
  - Using
  - Not using

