### 3. STUDY DESIGN

This is a multi-center, double-blind, randomized, placebo-controlled, parallel-group study in patients with probable DLB who are either not receiving therapy for DLB or are receiving a stable regimen of standard therapy for DLB. The efficacy and safety of Intepirdine at doses of 70 mg and 35 mg daily will be evaluated over a 24-week treatment period. All subjects who are on stable doses of other therapies to treat cognitive deficits and/or hallucinations associated with DLB will continue to remain on them for the duration of the study.

Approximately 240 subjects will be randomized. The randomization ratio will be 1:1:1 (70 mg Intepirdine: 35 mg Intepirdine: placebo). Double-blind treatment will be administered as follows:

- 70 mg Intepirdine (Test therapy): Intepirdine 70 mg given as two tablets of intepirdine 35 mg
- 35 mg Intepirdine (Test therapy): Intepirdine 35 mg given as one tablet of intepirdine 35 mg and one tablet of placebo
- Placebo (Reference): Matching placebo, given as two tablets of placebo

The primary endpoint (UPDRS Part III) and the secondary endpoints (ADAS Cog 11 and CIBIC+) will be measured after 24 weeks of treatment. Study participation will last approximately 32 weeks: 0 to 4 weeks for Screening, a 2-week Single-Blind Run-In Period to evaluate baseline status, a 24-week randomized, double-blind, placebo-controlled Treatment Period and a 2-week Safety Follow-up Period for subjects who do not enter the extension study RVT-101-2002.

[figure not shown]
There will be weekly clinical assessments for the first two weeks of double-blind treatment, bi-weekly assessments thereafter until 12 weeks post-randomization and every six weeks thereafter. For certain visits (Visits 5, 7 and 9), subjects may have the option of whether to have assessments performed at the clinical study site or by a trained, visiting nurse in their own home.

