## 6. SAMPLE SIZE CONSIDERATIONS

The sample size is based on assumptions of treatment benefit for one primary endpoint, the UPDRS- III total score. A sample size of 70 subjects per treatment group will allow a treatment difference of 4 points between placebo and active treatment in the change from baseline in UPDRS- III score to be detected with 88% power and a 0.05 significance level assuming an underlying standard deviation (SD) of 7.5

There are two secondary endpoints:

- ADAS-Cog 11 total score. A sample size of 80 subjects per treatment group will allow a treatment difference of 3 points between placebo and active treatment in the change from baseline in ADAS-Cog-11 score to be detected with 88% power and a 0.05 significance level assuming an underlying standard deviation (SD) of 6. Under the assumptions of a 2.5, 2.0 and 1.5 point treatment effect, the power is 74%, 55% and 35%, respectively.
- CIBIC+. A sample size of 80 subjects per treatment group will allow a treatment difference of 0.5 points between placebo and active treatment in the observed values in the CIBIC+ to be detected with 91% power and a 0.05 significance level assuming an underlying standard deviation (SD) of 0.95. Under the assumptions of a 0.4 and 0.3 point treatment effect, the power is 75% and 51%, respectively.

Randomization will be stratified according to Baseline MMSE score in the groupings of 14-17 points, 18-21 points and 22-26 points and according to whether subjects are or are not taking a cholinesterase inhibitor as a concomitant medication.

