## 7. GENERAL CONSIDERATIONS FOR DATA ANALYSES AND HANDLING

The primary statistical framework will be to test the superiority of Intepirdine over placebo. The null hypothesis is as follows, with a significance level of  $\leq 0.05$  needed for the null hypothesis to be rejected.

- There is **NO** statistically significant difference between Intepirdine and placebo in the mean change from baseline to Week 24 in the UPDRS- III.
- There **IS** a statistically significant difference between Intepirdine and placebo in in the mean change from baseline to Week 24 in the UPDRS- III.

The individual Intepirdine arms will be tested, as follows:

- Intepirdine 70 mg vs placebo
- Intepirdine 35 mg vs placebo

All hypothesis tests will be 2-sided, performed at the 5% level of significance.

The primary endpoint needs to achieve a significance level of 0.05 within an Intepirdine dose to allow for testing of the secondary endpoints within that dose.

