#### 9.3.1. MMRM

Primary treatment comparisons between Intepirdine and placebo will be performed on the change from Baseline to Week 24 using an MMRM with restricted maximum likelihood estimation, an unstructured covariance matrix, and the Kenward-Roger approximation for denominator degrees of freedom. The model will include terms for treatment, visit, treatment by

visit interaction, pooled geographic region, baseline MMSE score, the baseline value, and the baseline value by visit interaction.

- The region by treatment interaction term will be evaluated at the 10% level of significance; if the interaction term is found to be significant, it will be included in the MMRM model. Note, this applies to ALL MMRM models.
  - For the by-region Subgroup analyses, where, because the subgroup analyses by Region only include 1 region, the interaction makes no sense. The same MMRM model is also used for subgroups for the primary efficacy endpoint, as appropriate.

As additional supportive information, treatment differences at *each post baseline visit* will also be derived using the MMRM model; however, primary inferences will be drawn from treatment differences derived from the MMRM models at Week 24.

The estimated treatment difference (“Intepirdine 35mg – Placebo” and “Intepirdine 70mg – Placebo”) at each visit will be displayed in the summary of statistical analysis together with the 95% confidence interval and the associated p-value.

No imputation of the missing values will be performed for the primary analyses, ie, the data used in the analysis will be the actual observed responses at each visit.

Least Squares Means for each visit will also be presented with the standard error and the number of subjects contributing to the Least Squares Means. Least Squares Means and estimated treatment differences for each visit and the associated 95% confidence interval will be displayed graphically.

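### Outside region, subgroups are analysed by separate MMRM fits with no estimate of how the treatment effect differs between levels

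*SAP*

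**What the plan says.** SAP 7.8 concedes that the trial lacks power for subgroups and then commits that "the primary and secondary efficacy endpoints will be analyzed by defined subgroups". It lists baseline UPDRS (two cuts), baseline MMSE (14-19 and 20-26), region, age (two cuts), gender, race, ethnicity, cholinesterase inhibitor use (with donepezil and rivastigmine as single levels) and anti-parkinsonian use. Subgroups holding under 10% of randomised subjects may be skipped, and others may be added depending on the data.

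SAP 9.3.1 gives the model: "The same MMRM model is also used for subgroups for the primary efficacy endpoint, as appropriate". It notes that a by-region run contains only one region, which confirms that each level is fitted separately. The stated output is the treatment difference, its 95% CI and a p-value. For the secondary endpoints, SAP 9.4.1 calls for similar MMRM methods.

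The same section tests treatment by region at the 10% level in every MMRM and keeps the term if it is significant. The sample code in SAP 9.3.1.1 fits it. No corresponding term appears for any other subgroup factor.

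Randomisation (SAP 6) was stratified by "Baseline MMSE score in the groupings of 14-17 points, 18-21 points and 22-26 points" and by cholinesterase inhibitor use.

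**The concern.** The usual reason for a subgroup table is to judge whether the effect varies between kinds of patient. That question is answered by the difference between the level-specific effects and its uncertainty. This plan produces each level's effect and p-value but, outside region, not the difference. A reader given two p-values tends to compare them, and significance in one level without significance in the other is not evidence that the effects differ.

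The primary inference is not at stake. What is at stake is what the subgroup output can support, for example if it informs the choice of population for a later trial.

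**Working it through.** **Inputs.** Two-sided 5% tests (SAP 7: "All hypothesis tests will be 2-sided, performed at the 5% level of significance"). For UPDRS-III, SAP 6 states "A sample size of 70 subjects per treatment group will allow a treatment difference of 4 points between placebo and active treatment", "to be detected with 88% power and a 0.05 significance level assuming an underlying standard deviation (SD) of 7.5". Allocation is 1:1:1, and SAP 3 states "Approximately 240 subjects will be randomized", or 80 per arm. The documents give no subgroup sizes, so a range of splits is shown. The Week 24 MMRM contrast is approximated by a two-sample comparison.

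**Reproducing the plan's figure.** SE = 7.5 × √(2/70) = 1.268. Power = Φ(4/1.268 − 1.960) = Φ(1.195) = 88.4% (88.0% with the noncentral t). This matches the stated 88%.

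**Power within one half of an even split (35 per arm).** SE = 7.5 × √(2/35) = 1.793. Power = Φ(4/1.793 − 1.960) = Φ(0.271) = 60.7% (59.5% with the t).

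**Chance that exactly one level is significant when the true effect is 4 points in both.** The levels share no patients, so the chance is p1(1 − p2) + p2(1 − p1).

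- Even split: 2 × 0.607 × 0.393 = 47.7% (48.2% with the t). Both are significant in 36.8% and neither in 15.5%.
- 70:30 split (49 and 21 per arm): power 75.2% and 40.8%, so 0.752 × 0.592 + 0.408 × 0.248 = 54.6%.
- 90:10 split (63 and 7 per arm): power 84.9% and 16.8%, giving 73.2%.
- At 80 per arm: 44.6% (even), 52.7% (70:30) and 74.7% (90:10).
- Secondary endpoints at their design values, 40 per arm in each half: ADAS-Cog 11 (3 points, SD 6) 47.6%; CIBIC+ (0.5 points, SD 0.95) 45.3%.
- With no effect anywhere: 2 × 0.05 × 0.95 = 9.5%.

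**The between-level contrast.** For an even split at 70 per arm, SE = 7.5 × √(2/35 + 2/35) = 2.535, so the 95% half-width is 1.96 × 2.535 = 4.97 points. By construction a 0.05 test of this contrast flags a uniform effect about 5% of the time (5.1-5.3% in simulation). Its power for a true 4-point difference between levels is 35% at 0.05 and 47% at 0.10. At 80 per arm the SE is 2.37 and the power 39% and 52%.

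**The MMSE cut, checked separately.** This was a simulation with 4,000 runs per cut, 70 per arm, stratified allocation, ANCOVA within each level, a uniform 4-point effect, and MMSE assumed uniform over 14-26.

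| Cut | Exactly one level significant | Interaction flagged | Mean departure from 50:50, lower level |
|---|---|---|---|
| 17/18 (stratum boundary) | 55.7% | 5.3% | 0.6 points |
| 19/20 (planned) | 48.5% | 5.1% | 2.1 points |
| 21/22 (stratum boundary) | 50.0% | 5.2% | 0.4 points |

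The planned cut gives no more discordance than the stratum boundaries.

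**Number of comparisons.** The listed levels total 2+2+2+3+2+2+2+2+2+2+1+1+2 = 25. With three endpoints and two doses, that is at most 150 dose-versus-placebo MMRM comparisons at Week 24.

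**The case against.** The best defence is that the SAP never says it will judge subgroups by significance in one level and not another. It admits the lack of power, keeps subgroups out of the testing hierarchy, and prints a CI for each level. That stands: the 48% measures a reading rule the SAP leaves open, not one it adopts. The lack-of-power statement, however, warns of missed effects and does not supply a contrast.

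Several stronger readings are tempting but not supported.

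- *That no interaction is examined at all.* Treatment by region is tested in every MMRM. It is a model-building step for one factor, and the sample code gives it no visit term, so it is not a Week 24 contrast.
- *That the output cannot show whether a difference is real.* For two separately fitted levels, the difference and its SE, √(SE1² + SE2²), can be worked out from the planned estimates and intervals. The plan omits the contrast; it does not prevent it.
- *That the MMSE cut creates false differences.* The simulation shows otherwise. Only the 18-21 stratum is divided, the model adjusts for baseline MMSE, and comparisons within a baseline subgroup remain randomised.
- *That 150 tests will be run.* This is a ceiling: small levels may be dropped, and SAP 7.5 does not assess 35 mg if 70 mg fails on the primary endpoint.
- *That interaction tests would cure multiplicity.* Ten independent ones at 0.05 give 1 − 0.95^10 = 40% chance of at least one false signal.

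Late-added subgroups are partly covered. Protocol 10.4.6 treats analyses outside the SAP as post hoc, and SAP 7.3 requires deviations to be identified in the study report. But SAP 7.8 itself permits additions, so a late subgroup could pass as prespecified.

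**Conclusion.** The point holds as a cheap improvement to an exploratory analysis. For every subgroup factor except region, the plan gives within-level effects and p-values but no estimate of the difference between levels. The within-level fit is explicit for the primary endpoint; for the secondary endpoints it is read from SAP 7.8 and 9.4.1 together. At the design values, a uniform effect would leave exactly one of two levels significant in about 45-55% of cases for splits between 50:50 and 70:30, and more often for lopsided ones.

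These figures rest on the sample-size effect and SD being true, on assumed splits, and on a two-sample approximation to the MMRM.

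A minor separate point: the MMSE cut of 14-19/20-26 does not follow the randomisation strata. That slightly weakens guaranteed arm balance and does nothing more.

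**What to change.** In SAP 7.8, before unblinding:

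- For each subgroup factor, fit one MMRM on the full relevant population: the UPDRS Primary Analysis Population for UPDRS-III and the ITT Population for ADAS-Cog 11 and CIBIC+. Add the subgroup and subgroup-by-visit terms, with treatment-by-subgroup and treatment-by-subgroup-by-visit.
- Report the Week 24 effect in each level with its 95% CI, and the difference between levels with its 95% CI and interaction p-value.
- State the comparison group for the donepezil and rivastigmine levels, since no interaction is defined without one.
- Label any subgroup added later as post hoc.
- Optionally, use the randomisation strata for the MMSE subgroup.

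The cost is SAP wording and a little programming; treatment by region is already coded. The drawback is imprecision: the half-width of about 5 points for an even split exceeds the 4-point design effect. The contrasts should therefore be read from their intervals as exploratory, and a non-significant interaction should not be taken as proof of a uniform effect.

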## **8. STUDY POPULATION**

### **8.1. Subjects Disposition**

The total number of subjects that participated in the study will be summarized, including whether they were randomized or not. A tabulation will be provided for the number of subjects screened and screen-failed prior to the Placebo Run-in period. The denominator for those outcomes for this analysis will be the Screened Population.

The number subjects entering the Placebo Run-in, number subjects not completing the Placebo Run-in (and reasons for not completing) will be presented, using the Placebo Run-in Population as the denominator.

The number patients randomized, as well as the number of patients in the analysis populations (Safety, ITT, etc.) will be presented for the Randomized Population. The following will also be presented for the Randomized Population:

- A tabulation of the number of subjects randomized in each country will be provided. This tabulation will also include the pooled center counts (number of patients in each of the pooled/geographic region-based centers).
- An overall summary of the number and percentage of subjects who completed or discontinued from the Treatment Period will be displayed by treatment group. Reasons for discontinuation during the Treatment Period will be presented in the order they are displayed in the CRF. Subjects who discontinued from the Treatment Period will be listed by treatment group and subject.
- A cumulative distribution plot of the time to discontinuation during the Treatment Period will be provided and will include all treatment groups to allow for a visual inspection of the time to discontinuation. A similar plot will be provided for those patients who discontinue due to an on-treatment adverse event. The denominator for this plot will be the underlying population (and thus ‘censoring’ will not be applied).

### **8.2. Screen Failures**

Screen failure data will be tabulated by reason patients were found to not be eligible for the study. Patients may have screen failed due to any of the inclusion/exclusion criteria reasons as well as:

- Loss to follow-up
- Deviation/noncompliance with the protocol
- Adverse event
- Sponsor termination of the patient from the study
- Investigator decision
- Caregiver consent withdrawn
- Subject consent withdrawn

A listing of reasons of screen failures will be provided.

### **8.3. Demographic and Baseline Characteristics**

Demographic data will be summarized for the ITT Population and the Safety Population.

- All demographic data [eg, age, gender, race, baseline MMSE stratum per the randomization, AChEI use (yes/no)] will be tabulated, along with the defined subgroups (see [Section 7.8](#)).
- Dementia with Lewy Bodies diagnosis information will be summarized in a similar fashion.
- Other characteristics collected on the CRF will be summarized by the number and percentage of subjects, or as appropriate.
- Baseline values for the efficacy endpoints will be provided as part of the baseline characteristics assessment.
- Details of the primary caregiver (relationship to subject, cohabitating with subject, # hours spent with subject, # days spent with subject) will be included in a tabulation.
- A CT scan or MRI may be performed at screening; outcomes will be listed.

#### **8.3.1. Lewy Body Composite Risk Score (LBCRS)**

The LBCRS is a scale that has been shown to help discriminate DLB from other causes of dementia, such as Alzheimer's disease, using a cut-off score of 3 ([Galvin 2015](#)). LBCRS will be administered during screening to collect information regarding the clinical presentation of DLB symptoms.

Ten questions are completed by a clinician after interview with patient and caregiver and a complete physical and neurological exam. The clinician rates the presence or absence of physical signs and can elicit information from either the patient or caregiver regarding the presence or absence of symptoms. 1 point is awarded for each "Yes" response.

The LBCRS total score is the sum of the items 1 through 10, with scores ranging from 0 to 10. Interpretation as to whether the patient is a Lewy Body 'case' is as follows:

- 0 to 2: Non-Lewy Body Case
- >2: Probably Lewy Body Case

The number (%) of patients meeting the threshold for >2 on the LBCRS will be tabulated, as well as the distribution of scores (ranging from 0 to 10). These data will be presented in the baseline characteristics table and will also be listed.

### **8.4. Subject Inclusion and Exclusion Criteria**

Patients not meeting eligibility criteria will be listed.

### **8.5. Medical History**

Medical history will be collected and coded using the Medical Dictionary for Regulatory Activities (MedDRA), using Axovant Sciences coding conventions.

A tabulation displaying medical history will be provided and will form the basis for discussion regarding the medical history of patients enrolled in this study.

## 8.6. Prior and Concomitant Medications

Medication verbatim text will be coded using the WHO ATC classification ([http://www.whocc.no/filearchive/publications/1\\_2013guidelines.pdf](http://www.whocc.no/filearchive/publications/1_2013guidelines.pdf)).

Medications will be tabulated as:

- Prior medications
- Concomitant medications
  - Single-blind run-in
  - Double-blind period
  - Post-treatment period
- New-onset concomitant medications (those starting only after the date of first dose of double-blind study medication)

Medications received prior to the date of first dose of single-blind study medication are considered as prior medications. Medications will be considered as concomitant if the start date of the medication is on or after the date of first intake of investigational product or if the start date is prior to the first date of investigational product but the medication is ongoing during the treatment period in the study.

A concomitant medication can be counted in more than one period.

Note that multiple drug use (by preferred name) will be counted once only per subject in the tabulations. No inferential statistics are planned.

A listing of non-medication therapy will be provided.

## 8.7. Extent of Exposure

Duration of exposure for the Safety Population during the Double-Blind Treatment Period will be calculated as follows:

- Duration of exposure in days = (Double-Blind Treatment stop date – Double-Blind Treatment start date) + 1

Total dose will be calculated as:

- Total Dose = duration of exposure × dose.

Duration of exposure and Total dose will be tabulated descriptively. Exposure also will be categorized as:

- 0 to 2 weeks
- >2 to 4 weeks
- >4 to 8 weeks

- >8 to 12 weeks
- >12 to 16 weeks
- >16 to 24 weeks
- >24 weeks

Exposure will also be categorized as <23 weeks and  $\geq$ 23 weeks.

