IP for the Double-Blind Treatment Period (Weeks 0 to 24) will be supplied at Visits 3, 6, 8, 10, and 11. At each dispensing visit during the Treatment Period, subjects will be given an IP kit containing 2 bottles of IP. Depending on treatment assignment, subjects will receive either two bottles of 35 mg RVT-101 tablets, one bottle of 35 mg RVT-101 tablets and one bottle of placebo tablets, or two bottles of placebo tablets. Each bottle will contain 50 tablets, which is sufficient for 4 weeks plus 22 days overage (V3, V6, V8) and for 6 weeks plus 8 days overage (V10 and V12). Subjects will be instructed to take two tablets of IP daily at bedtime with or

without food; this will consist of one tablet from each of the two bottles in the kit. New bottles of IP will not be dispensed at Visits 4, 5, 7, and 9, however, drug accountability will be checked, and subjects will be re-dispensed the IP bottles they received at the previous dispensing visit. All subjects and their caregivers should be instructed to bring IP bottles, with any unused drug, to each visit. It is important that drug accountability is checked individually for each of the two dispensed bottles.

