## **7.6. Compliance with Investigational Product Administration**

When subjects are dosed at the site, they will receive IP directly from the investigator or designee, under medical supervision. The date and time of each dose administered in the clinic will be recorded in the source documents. The dose of IP and study subject identification will be confirmed at the time of dosing by a member of the study site staff other than the person administering the IP.

Subjects and caregivers should be instructed that subjects are to take one tablet of IP from each bottle before bedtime. Subjects and caregivers must be made aware that subjects are not to take two tablets from the same bottle, and are not to combine pills from the two bottles into a single storage bottle. The contents of each bottle must remain distinct. Product administration instructions should be reinforced at each visit.

Every effort should be made to encourage subject compliance with the dosage regimen as per protocol for IP. The investigator is responsible for discussing methods to ensure high treatment compliance with patients and caregivers before randomization. All subjects and their caregivers should be instructed to return IP bottles with any unused drug at each visit to the investigator or designee. A record of the supplies dispensed, taken, and returned will be made in the eCRF at each visit. The investigator or designee is responsible for reconciling the number of tablets returned with the expected number of tablets to be taken by a study subject and accounting for any discrepancies for each of the two bottles.

Subjects should be withdrawn from the study where there has been a failure to take blinded IP for a period exceeding 7 consecutive days. While interruptions in IP administration should be avoided wherever possible, short-term interruptions ( $\leq 7$  days) due to forgetfulness, caregiver

illness or absence, a pause in IP administration required during an intervention, hospitalization, or while a subject considers the study continuation, or for any other reason are not grounds for automatic withdrawal but should be assessed by the investigator.

Other major protocol violations as well as use of excluded drugs (see [Section 7.9.2](#)) may be cause for discontinuation of IP or withdrawal from the study.

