- Completers (CS) Population: ITT subjects who have completed the Week 24 visit with non-missing endpoints for all three variables, the UPDRS-III, ADAS-Cog 11, and CIBIC+. This population will be used for supportive analysis of all efficacy variables except the UPDRS variables.
- UPDRS Completers Primary Analysis Population: UPDRS Primary Analysis Population Patients who have a Week 24 UPDRS Part III value. This will be run only on the UPDRS Part III and Part 5 variables.
- Pharmacokinetics (PK) Population: All subjects in the Safety Population who undergo plasma PK sampling and have at least one post-baseline evaluable PK concentration result.
- Per-Protocol (PP) Population: Subjects in the ITT Population who have no major protocol violations. The PP Population will not be analyzed if this population comprises more than 95% or less than 50% of the ITT Population. This population will be used for confirmatory analysis all efficacy variables except the UPDRS variables. The PP Population will be identified prior to breaking the study blind. Major protocol violations will be defined as follows:
  - Subject had >7 consecutive days interruption in double-blind study medication

- Treatment with excluded concomitant medications during the double-blind treatment period.
  - If taking an acetylcholinesterase inhibitor, subject had a change in AChEI dose or frequency during the double-blind treatment period.
  - Significant study drug administration errors.
  - Invalid baseline primary or secondary efficacy assessment.
  - Subject does not have MMSE score 14-26 inclusive at Screening and Baseline
  - Subject's baseline MMSE declined by 4 or more points from Visit 2 (Run-in) to Baseline
  - Evidence of other causes of dementia other than DLB as the primary cause
  - History or presence of significant medical or psychiatric condition at Screening.
  - Subject does not live with (or have substantial Periods of contact with) a regular caregiver [at least 10 hours total and at least 3 days per week]).
  - Subject is <80 % compliant or > 120% compliant between Visit 11 (Week 18) and Visit 12 (Week 24) with study drug. Patients who fail to return their bottle (and thus compliance cannot be determined) will be assumed to have been compliant for purposes of the Per Protocol population.

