## 8.8. Treatment Compliance

Compliance with study drug will be assessed over the Double-Blind Treatment Period and Run-In Period using drug dispensing records. Treatment compliance will be computed by determining the number of tablets taken relative to the number of tablets expected. Patients are expected to take two tablets per day, one from each of two bottles.

Treatment compliance based on the drug accountability will be calculated as follows:

- compliance (%) = (number of tablets taken)/(number of tablets expected)\*100
  - number of tablets taken = the number of tablets dispensed – the number of tablets returned
  - number of tablets expected = (date of the last dose - date of the first dose+1)

Summary of treatment compliance will be presented by treatment group, between Week 18 and 24 as well as overall. The number and percentage for compliance expressed as a categorical variable (<80%,  $\geq$ 80% to  $\leq$ 120%, and >120%) will be also presented by treatment group.

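### SAP Total Dose ignores missed tablets and bottle mix-ups, and the compliance formula does not say whether the two bottles are counted separately or together

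*SAP*

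**What the plan says.** **Exposure (SAP 8.7).** Duration is counted from first to last day: "Duration of exposure in days = (Double-Blind Treatment stop date – Double-Blind Treatment start date) + 1". Cumulative dose follows as "Total Dose = duration of exposure × dose". The word dose is not defined there; the assigned daily dose is the natural reading. Both quantities are tabulated descriptively.

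**Compliance (SAP 8.8).** The text states "Patients are expected to take two tablets per day, one from each of two bottles". The numerator is "number of tablets taken = the number of tablets dispensed – the number of tablets returned". The denominator is "number of tablets expected = (date of the last dose - date of the first dose+1"), that is, one tablet per day. Nothing says whether the counts are per bottle or summed over both.

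**Per-protocol rule (SAP 7.4).** One major violation reads "Subject is <80 % compliant or > 120% compliant between Visit 11 (Week 18) and Visit 12 (Week 24) with study drug". Significant errors in administering study drug are another, without a definition. Both per-protocol populations must be fixed before the blind is broken.

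**Supply and accountability (Protocol 7.1, 7.6).** Each kit holds two 50-tablet bottles. In the 35 mg arm one is active and one is placebo. On counting, the protocol says "It is important that drug accountability is checked individually for each of the two dispensed bottles". On use, it says "Subjects and caregivers must be made aware that subjects are not to take two tablets from the same bottle". Section 7.6 also has the investigator reconcile returned against expected tablets for each bottle.

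**The concern.** In the 35 mg arm the dose depends on which bottle each tablet comes from, and the population is cognitively impaired. The protocol foresees the mix-up, warns against it and requires counts that would show it. The SAP derivations do not use those counts for dose, and may not use them for compliance. Total Dose as defined is a planned quantity under a label that reads as dose received. Interruptions of up to 7 days, which Protocol 7.6 says should be avoided but which do not lead to automatic withdrawal, are counted as if the tablets had been taken.

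At stake are the exposure table, the compliance table, and which subjects stay in the per-protocol populations.

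**Working it through.** **Inputs.** 168 days of treatment; dispensing at Visits 3, 6, 8, 10 and 11, giving intervals of 28, 28, 28, 42 and 42 days; 50 tablets per bottle, two bottles per kit; 35 mg per active tablet (Protocol 7.1 and schedule). The compliance band is 80–120% (SAP 7.4).

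**Supply figure reproduced.** At one tablet per bottle per day, 50 − 28 = 22 and 50 − 42 = 8 days of overage, as Protocol 7.1 states.

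**Total Dose.** The SAP formula gives 168 × 70 = 11,760 mg and 168 × 35 = 5,880 mg, whatever was taken.
- With 80% of tablets taken, dose received is 0.8 × 11,760 = 9,408 mg and 0.8 × 5,880 = 4,704 mg. The overstatement is 1/0.8 − 1 = 25%.
- With 50% taken, it is 1/0.5 − 1 = 100%.
- With one 7-day gap, it is 168/161 − 1 = 4.3% (490 mg at 70 mg; 245 mg at 35 mg).

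**Compliance under the possible readings.** In a mix-up here, two tablets a day come from one bottle until it is empty, then from the other. Over 28 days that is 50 and 6 tablets; over 42 days, 50 and 34.

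| Behaviour | Pooled ÷ days | Pooled ÷ (2 × days) | Per bottle ÷ days |
|---|---|---|---|
| Correct use | 200% | 100% | 100% / 100% |
| 80% of tablets taken | 160% | 80% | 80% / 80% |
| Half of tablets taken | 100% | 50% | 50% / 50% |
| Mix-up, 28 days | 56/28 = 200% | 56/56 = 100% | 50/28 = 179%; 6/28 = 21% |
| Mix-up, 42 days | 84/42 = 200% | 84/84 = 100% | 50/42 = 119%; 34/42 = 81% |

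In either pooled column the mix-up equals correct use: both 200%, or both 100%. Changing the denominator alone therefore does not reveal it. Per-bottle counts do, but in a 42-day interval both bottles stay inside 80–120%. Weeks 18–24, the only period in the per-protocol compliance rule, is such an interval.

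**Limits set by bottle size (35 mg arm, two tablets a day).**
- Most active tablets: 5 × 50 = 250, so 250 × 35 = 8,750 mg, a mean of 52.1 mg/day.
- Fewest: 6 + 6 + 6 + 34 + 34 = 86, so 86 × 35 = 3,010 mg, a mean of 17.9 mg/day.
- SAP 8.7 reports 5,880 mg in both cases. The difference is 2,870 mg either way, or 2,870/5,880 = 49% of the reported figure.

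**The case against.** The strongest reply is that little depends on Total Dose. It is descriptive. Adverse event incidence uses numbers of subjects in the Safety Population. Efficacy subjects are grouped by randomised treatment. Exposure–response work uses model-based AUC, Cmax and Cmin. All of this stands and limits the point to reporting and per-protocol status.

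Second, missed tablets are not lost from the report: SAP 8.8 uses returned counts and tabulates compliance overall and for Weeks 18–24. This also stands; the omission is confined to Total Dose.

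Third, the SAP never says the bottles are pooled. One expected tablet per day fits a per-bottle count at least as well as a pooled one. That is correct, and what can be shown is an ambiguity. But the same section speaks of two tablets a day, so two programmers could reasonably implement it differently, and SAP 7.3 gives the SAP precedence over analyses described in the protocol.

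Fourth, a mix-up leaves evidence: site reconciliation by bottle, listings of all CRF data, plasma concentrations, and the per-protocol criterion on administration errors. This rules out saying that it would pass without trace, but none of these is a defined check. The criterion has no definition, scheduled plasma samples are at Weeks 4 and 8 only, and the overdose listing starts above 105 mg in 24 hours, which a 35 mg subject taking two active tablets would not reach.

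**Conclusion.** The point holds as a reporting defect. Followed exactly, SAP 8.7 gives planned dose over calendar time, 25% above dose received at 80% of tablets taken. SAP 8.8 leaves the unit of count open, and any pooled version cannot separate a two-a-day bottle mix-up from correct use.

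Three stronger readings should be resisted.
- A reader might infer that a mixed-up 35 mg subject is shown as compliant. Pooled as literally written, that subject scores 200% and falls above 120%, as does a perfect taker; 100% needs a factor of two that the SAP denominator lacks.
- A reader might infer that such a subject could receive 70 mg or 0 mg daily throughout. At two tablets a day, bottle size limits the 168-day total to 3,010–8,750 mg; 0 mg throughout would require never using the active bottle.
- A reader might infer that the primary comparison or safety rates are biased by the formula. Neither uses Total Dose, and any blurring of the dose arms would arise in conduct, not from section 8.7.

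Assumptions: visits on nominal days, the last kit dispensed at Visit 11, no tablets carried over between kits, and accurate returned counts. The documents give no frequency of mix-ups, so the range is a bound and not an expected error.

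**What to change.** 1. **SAP 8.7.** After unblinding, define Total Dose as 35 mg × tablets taken from active bottles, summed over dispensing intervals, and average daily dose as Total Dose ÷ duration. Show subjects with unreturned bottles as having unknown dose.
2. **SAP 8.8.** Compute compliance per bottle per dispensing interval against one tablet per bottle per day, and overall against two tablets per day. State both denominators.
3. **Bottle imbalance.** Before unblinding, and in all arms alike, list subjects whose two bottle counts differ by more than a pre-stated amount, and review them blinded under the existing per-protocol criterion on study drug administration errors. The 80–120% band cannot do this alone, because of the 119%/81% result. Flagging only 35 mg subjects would need treatment codes and would conflict with SAP 7.2 and 7.4, which fix per-protocol exclusions before unblinding.

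The cost is SAP wording and a little programming, since the protocol already requires counts by bottle. It relies on those counts being stored per bottle and traceable to bottle contents once codes are released. Some subjects will have unknown dose because bottles were not returned; that is more accurate than crediting them with the full planned amount.
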